## 10.0 EVALUATION CRITERIA

## 10.1 Common Terminology Criteria for Adverse Events (CTCAE)

This study will utilize the CTCAE of the National Cancer Institute (NCI) for toxicity and performance reporting. A copy of the CTCAE version 4.0 can be downloaded from the NCI Website at: (http://ctep.cancer.gov/protocolDevelopment/electronic\_applications/docs/ctcaev4.pdf). Additionally, toxicities are to be reported on the appropriate case report forms.

## 11.0 ADVERSE EVENT REPORTING REQUIREMENTS

## 11.1 Purpose

Adverse event data collection and reporting, which are required as part of every clinical trial, are done to ensure the safety of patients enrolled in the studies as well as those who will enroll in future studies using similar agents.

## 11.2 Determination of Reporting Requirements

Reporting requirements may include the following considerations: 1) the characteristics of the adverse event including the *grade* (severity); 2) the *relationship to the study therapy* (attribution); and 3) the *prior experience* (expectedness) of the adverse event.

Commercial agents are those agents not provided under an IND but obtained instead from a commercial source. In some cases an agent obtained commercially may be used for indications not included in the package label. In addition, NCI may on some occasions distribute commercial supplies for a trial. Even in these cases, the agent is still considered to be a commercial agent and the procedures described below should be followed.

Determine the prior experience Expected events are those that have been previously identified as resulting from administration of the agent. An adverse event is considered *unexpected*, for reporting purposes only, when either the type of event or the severity of the event is not listed in:

- the current known toxicities for each commercial agent as provided in the Drug
  Information for Commercial Agents Used by the Children's Oncology Group posted on the COG Website; or
- the drug package insert.

#### Secondary Malignancy

A **secondary malignancy** is a cancer caused by treatment for a previous malignancy (eg, treatment with investigational agent/intervention, radiation or chemotherapy). A metastasis of the initial neoplasm is not considered a secondary malignancy.

All secondary malignancies that occur following treatment need to be reported via CTEP-AERS. Three options are available to describe the event:

- Leukemia secondary to oncology chemotherapy
- Myelodysplastic syndrome
- Treatment related secondary malignancy
- 11.3 **Reporting of Adverse Events for Commercial Agents CTEP-AERS abbreviated pathway** Commercial reporting requirements are provided in Table B. The commercial agent(s) used in this study are listed in the front of this protocol immediately following the Study Committee roster.
  - COG requires the CTEP-AERS report to be submitted within 7 calendar days of learning of the event.
  - Use the NCI protocol number and the protocol-specific patient ID provided during trial registration on all reports.

**CTCAE term (AE description) and grade:** The descriptions and grading scales found in the NCI Common Terminology Criteria for Adverse Events (CTCAE) version 4.0 will be utilized for AE reporting and are located on the CTEP website at:

http://ctep.cancer.gov/protocolDevelopment/electronic\_applications/ctc.htm. All appropriate treatment areas should have access to a copy of the CTCAE.

#### Table B

Reporting requirements for adverse events experienced by patients on study who have NOT received any doses of an investigational agent on this study.

CTEP-AERS Reporting Requirements for Adverse Events That Occur During Therapy With a Commercial Agent or Within 30 Days

Attribution	Gra	Grade 5	
	Unexpected	Expected	
Unrelated or			CTEP-AERS
Unlikely			
Possible,			~~~~
Probable,	CTEP-AERS		CTEP-AERS
Definite			

This includes all deaths within 30 days of the last dose of treatment with a commercial agent, regardless of attribution. Any death that occurs more than 30 days after the last dose of treatment with a commercial agent which can be attributed (possibly, probably, or definitely) to the agent and is not due to cancer recurrence must be reported via CTEP-AERS.

## 11.4 Routine Adverse Event Reporting

**Note:** The guidelines below are for routine reporting of study specific adverse events on the COG case report forms and do not affect the requirements for CTEP-AERS reporting.

The NCI defines both routine and expedited AE reporting. Routine reporting is accomplished via the Adverse Event (AE) Case Report Form (CRF) within the study database. For this study, routine reporting will include all toxicities reported via CTEP-AERS and all Grade 4 and higher non-hematologic Adverse Events.

Note: During the infection observation period only (see definition Section 7.1.2), fever, febrile neutropenia and sepsis (of any grade) are captured as study endpoints and therefore should be excluded from routine AE reporting.

#### 12.0 RECORDS AND REPORTING

See the Case Report Forms posted on the COG Website with each protocol under "Data Collection/Specimens". A submission schedule is included.

## 12.1 **CDUS**

This study will be monitored by the Clinical Data Update System (CDUS). Cumulative CDUS data will be submitted quarterly to CTEP by electronic means. Reports are due January 31, April 30, July 31 and October 31. This is not a responsibility of institutions participating in this trial.

# 13.0 SPECIAL STUDIES SPECIMEN REQUIREMENTS

In order to allow central review of the stool and peri-rectal swab specimens, samples will be collected at each participating institution, and processed and shipped in transport media to the Microbiology Laboratory of [name], MPH at the Infectious Diseases Research Laboratory (IDRL) of the Children's Hospital of Pittsburgh.

## 13.1 Samples Collection and Shipping Procedures

#### 13.1.1 Collection

Collect perirectal, rectal or direct stool swab using any Dacron-tipped bacterial culture system (kits will not be provided). Stool or peri-rectal specimens will be obtained either by inoculation of a sterile dacron-tipped swab into stool in a diaper, or by placing a swab moistened with sterile saline into the peri-rectal area where it will be held in this position for 5 seconds. Ideally the surface of the swab should appear "dirty" after specimen collection. Once the specimen is collected the swab should be inserted into the swab's accompanying culture media sleeve. All specimens should be refrigerated immediately upon collection.

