#### See Section 5.0 for Dose Modifications based on Toxicities.

The therapy delivery maps (TDMs) for levofloxacin therapy are on the next 2 pages.

Prophylactic Therapy Delivery Map – AL Patients in Arm B	
Patients undergoing treatment for AL receive antibacterial prophylaxis during 2 consecutive cycles	
of chemotherapy.	Patient name or initials
	DOD

For each of 2 consecutive chemotherapy cycles, begin study treatment on Day 3 of systemic chemotherapy. Extensive details are in Section 4.0 (treatment overview). Cvcle: 1

This Therapy Delivery Map is on **one** (1) page.

		(-) F8-1		-,	
DRUG	ROUTE	DOSAGE	DAYS	IMPORTANT NOTES	OBSERVATIONS
Levofloxacin	PO*/IV  *Given PO if tolerated; otherwise by IV.	Age ≥ 6 months to < 5 years: 10 mg/kg twice daily ≥ 5 yrs: 10 mg/kg once daily	Daily beginning on Day 3 of systemic chemotherapy)^	^Continue until ANC is > 200/μL and rising post-nadir or Day 60 (from Day 1 of each cycle of systemic chemotherapy) if ANC > 200/μL is not reached or the day prior to the next cycle of chemotherapy.  Note age-based dosing	
 
a. History, physical, ht/wt, performance status
 
b. CBC, Cr (at intervals according to good patient care)
 
c. Optional peri-rectal swab or stool specimen (see Section 7.2)
 
† Infection information during infection observation period (see Section 7.1.2)
 

				Maximum per day: 500 mg if < 5 years of age, 750 mg if ≥ 5 years See Section 4.2 for rounding of oral doses	OBTAIN OTHER STUDIES AS REQUIRED FOR GOOD PATIENT CARE

		Htcr	n Wtkg	BSA	$_{\rm m}^2$	
Start Day	Stop Day Date	Age: $\geq$ 6 months to $\leq$ 5 years	Age: $\geq 5$ years	Studies †	Comments (Include any held doses, or dose modifications)	
Date (d/m/y)	(d/m/y)	LEVO^	LEVO^			
` **	• • • • • • • • • • • • • • • • • • • •	mgmg	mg			
		Enter calculated dose above an	d actual dose administered b	oelow		
0-3				a, b, c		
3 ( / / )	(_/_/)^	mgmg	mg			
(_/_/)	(_/_/)^	mgmg	mg			
(_/_/)	(_/_/)^	mgmg	mg			
(_/_/)	(_/_/)^	mgmg	mg			
Continue until ANC is > 200/uL and rising post-padir  ; see Section 4.1 for details regarding starting and stopping of levofloxacin						

Continue until ANC is  $> 200/\mu$ L and rising post-nadir'; see Section 4.1 for details regarding starting and stopping of levofloxacin. Levofloxacin should be discontinued immediately for any patient with confirmed tendinopathy (tendinitis or tendon rupture) (see Section 4.1).

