On the TDM, indicate each start and stop dates of levofloxacin. The subject may start and stop levofloxacin multiple times prior to meeting the criteria for completion of levofloxacin. Levofloxacin should be held when parenteral antibiotics are administered for other indications such as for empiric or therapeutic management of infection.

See Section 5.0 for Dose Modifications for Toxicities and the COG Website posted materials for Supportive Care Guidelines

Prophylactic Therapy Delivery Map – HSCT Patients in Arm B	
Patients undergoing HSCT receive antibacterial prophylaxis during 1 transplant procedure.	Patient name or initials
	DOB

Begin study treatment on Day -2 from stem cell infusion. Extensive details are in Section 4.0 (treatment overview).

This Therapy Delivery Map is on one (1) page.

DRUG	ROUTE	DOSAGE	DAYS	IMPORTANT NOTES	OBSERVATIONS
Levofloxacin	PO*/IV	Age	Daily beginning on	^Continue until ANC is $> 200/\mu L$	a. History, physical, ht/wt, BSA, performance
		$\geq$ 6 months to $\leq$ 5 years:	Day -2^	and rising post-nadir or HSCT	status
	*Given PO if	10 mg/kg twice daily		Day +60 if ANC > $200/\mu$ L is not	b.CBC, Cr (at intervals according to good
	tolerated;			reached	patient care)
	otherwise by IV.	≥ 5 yrs: 10 mg/kg once daily		Note age-based dosing	c. Optional peri-rectal swab or stool specimen (see Section 7.2)
				Maximum per day: 500  mg if < 5  years of age, $750 \text{ mg if} \ge 5 \text{ years}$	† Infection information during infection observation period (see Section 7.1.2)
				See Section 4.2 for rounding of oral doses	OBTAIN OTHER STUDIES AS REQUIRED FOR GOOD PATIENT CARE

		Ht	_cm	Wtkg	BSA	$m^2$
Start Day	Stop Day Date	Age: $\geq$ 6 months to	< 5 years	Age: ≥ 5 years	Studies †	Comments (Include any held doses, or dose modifications)
Date (d/m/y)	(d/m/y)	LEVO^		LEVO^		
` • •		mg	mg	mg		
		Enter calculated dos	e above and	actual dose administered	l below	
-3					a, b, c	
-2 # (_ /_ /)	_ (_ /_ /)^	mg	mg	mg		
	_ (_ /_ /)^	mg	mg	mg		
	_ (_ /_ /)^	mg	mg	mg		
(_/_/)	_ (_ /_ /)^	mg	mg	mg		
	Continue until ANC is $> 200/\mu$ L and rising post-nadir ^ ; see Section 4.1 for details regarding starting and stopping of levofloxacin.					
	Levofloxacin should be discontinued immediately for any patient with confirmed tendinopathy (tendinitis or tendon rupture) (see Section 4.1).					

#Stem cell infusion 2 days later on Day 0

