# 7.2 **Optional Study**

# 7.2.1 Study Design for Ancillary Study

As part of the ACCL0934 trial, an ancillary study will examine the association between receipt of prophylactic levofloxacin and colonization or infection with antimicrobial-resistant organisms. Stool or peri-rectal swabs will be collected for assessment of longitudinal changes in colonization including several clinically significant bacterial organisms (*E. coli, K. pneumoniae, P. aeruginosa,* and *S. mitis*) and evaluation for the presence of resistance for each of these organisms to levofloxacin and other commonly used antibiotics in pediatric oncology. In addition to screening for specific antibiotic resistance among the aforementioned organisms, screening for the presence of any carbapenem-resistant Enterobacteriaceae will also be performed on specimens collected at the end of each patient's reporting period (i.e. their second stool or perirectal swab).

All patients enrolled on ACCL0934 will be offered the opportunity to participate in this ancillary resistance study. Colonization of resistant organisms will be determined by either peri-rectal or stool swabs. In comparison to stool specimens, peri-rectal swabs are 90% sensitive and 100% specific in identifying the presence of fluoroquinolone resistant *E. coli.* Consequently, peri-rectal swabs will be the preferred method of resistance surveillance although an institution and/or patient may choose to use stool specimens as long as the method of collection is constant within an individual patient. If a stool specimen is chosen as the method of collection, but cannot be provided during a sampling period (for example, in the event of constipation), then a peri-rectal swab may be substituted.

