Stool specimens or peri-rectal swabs will be obtained at baseline and then at the time of resolution of neutropenia for each of the study cycles (twice for those with AL and once for those undergoing HSCT). Sample collection will be obtained within 1 week of count recovery defined as an ANC  $> 200/\mu$ L following the nadir. If a patient does not resolve their neutropenia, then the specimen should be obtained on Day 60 from the start of the infection observation period or within 2 days before the next chemotherapy cycle is initiated, whichever comes first. Figure 1 displays the planned specimen collection schema. Patients with AL will be followed for 2 cycles of chemotherapy resulting in 3 stool or peri-rectal specimens and those patients undergoing HSCT will be followed for 1 transplant procedure resulting in 2 stool or peri-rectal specimens.

[figure not shown]

Figure 1. Peri-rectal or stool specimen collection schema

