# 8.0 CRITERIA FOR REMOVAL FROM PROTOCOL THERAPY AND OFF STUDY CRITERIA

# 8.1 Criteria for Removal from Protocol Therapy

- a) Signs or symptoms suggestive of tendonitis or tendon rupture.
- b) Refusal of further protocol therapy by patient/parent/guardian.

\* Defined as ANC > 200/ $\mu$ L and rising post-nadir or Day 60 (from Day 1 of each cycle of systemic chemotherapy or HSCT Day +60) if an ANC > 200/ $\mu$ L has not been reached. For patients who begin their next cycle of chemotherapy before the ANC > 200/ $\mu$ L and before Day 60, the swab should be obtained prior to the first day of the next course of chemotherapy.

\*\*Baseline swabs can be performed anytime between the date of enrollment and Day 3 of chemotherapy for leukemia patients or Day -2 for HSCT recipients.

- c) Completion of planned study treatment.
- d) Physician determines it is in patient's best interest.

Patients who are off protocol therapy are to be followed until they meet the criteria for Off Study (see below). Follow-up data will be required unless consent was withdrawn.

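### Section 13.1.1 lists a rectal swab among the permitted samples, although the rest of the available plan provides only for stool or peri-rectal specimens

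*Combined protocol and SAP*

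**What the plan says.** Section 13.1.1 opens with this instruction to sites: "Collect perirectal, rectal or direct stool swab using any Dacron-tipped bacterial culture system". The sentence that follows describes how to take two kinds of specimen. One is a swab put into stool in a diaper. The other is obtained "by placing a swab moistened with sterile saline into the peri-rectal area where it will be held in this position for 5 seconds". It says nothing about a rectal swab, either to describe it or to exclude it.

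The design text in Section 7.2.1 names two methods: "Colonization of resistant organisms will be determined by either peri-rectal or stool swabs". It prefers the peri-rectal swab, allows stool instead, and makes the peri-rectal swab the fallback when stool cannot be produced. Both therapy delivery maps in Section 4.2 carry the entry "Optional peri-rectal swab or stool specimen". Section 13.1.2 gives two source categories for the label, stool and peri-rectal swab. Section 9.5.3.1 presents stool or peri-rectal sampling as simple and not invasive, and bases its expectation of 80% participation partly on that.

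On timing, Section 7.2.1 says "Sample collection will be obtained within 1 week of count recovery defined as an ANC" above 200/µL after the nadir. If neutropenia does not resolve, the sample is due on Day 60 "or within 2 days before the next chemotherapy cycle is initiated, whichever comes first". A footnote to Figure 1, printed with Section 8.1, says that when the next cycle starts before recovery and before Day 60, "the swab should be obtained prior to the first day of the next course of chemotherapy".

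**The concern.** Section 13.1.1 is the text that bedside staff follow. By naming rectal and perirectal side by side, it presents them as alternatives, so a site could reasonably conclude that a swab inserted into the rectum is allowed. On the plain meaning of the words, that is more invasive than a swab held in the peri-rectal area.

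The sample is optional and taken for research, and some of the children will be neutropenic or only just recovering when it is taken. A plan should not loosely permit a more invasive procedure than the one it describes and calls non-invasive. Two details nearby do not help: sites use their own culture systems because no kit is supplied, and staff are told that the swab should ideally look soiled, which could tempt someone to insert it when a peri-rectal swab comes out clean.

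**Working it through.** No figure in the plan depends on this point, so the check compares wording across the plan and then counts scheduled samples.

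**Step 1. Where each specimen type is named in the available text.**

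| Place | Specimen types named |
|---|---|
| 13.1.1, first sentence | perirectal, rectal, direct stool |
| 13.1.1, second sentence (technique) | stool, peri-rectal |
| 1.2.1 objective | peri-rectal |
| 4.2 delivery maps, AL and HSCT (2 places) | peri-rectal, stool |
| 7.1 evaluation table | peri-rectal, stool |
| 7.2.1 design and schedule (2 places) | peri-rectal, stool |
| 9.1 and 9.3.1.2 (2 places) | stool, peri-rectal |
| 9.5.2.5 and 9.5.3.1 (2 places) | stool, peri-rectal |
| 9.5.3.2 event rates and its AL continuation (2 places) | stool, peri-rectal |
| 13.0 introduction | stool, peri-rectal |
| 13.1.2 label | stool, peri-rectal |
| 13.2 carbapenem-resistance screening | stool, perirectal |

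Outside 13.1.1 the count is 1 + 2 + 1 + 2 + 2 + 2 + 2 + 1 + 1 + 1 = 15 places, and none names a rectal swab as a specimen. The only other appearance of the term is in the title of reference 57, which is not an instruction.

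**Step 2. Does the next sentence remove the option?** It gives technique for two methods only, so a site following it would not take a rectal swab. But it is worded as a description of stool and peri-rectal specimens and does not withdraw the third type just listed. The first sentence therefore still permits a type that has no technique, no label category and no place in the design text. A rectal swab would have to be labelled as one of the other two types, so the label could not show how often it was done.

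**Step 3. How many samples fall at or near neutropenia?** Section 7.2.1 plans 3 samples for an AL patient and 2 for an HSCT patient, and one of each is the baseline sample.

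- AL: 3 − 1 = 2 post-baseline samples.
- HSCT: 2 − 1 = 1 post-baseline sample.

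These are taken within a week of the count passing 200/µL or, without recovery, at Day 60 or before the next cycle. The figures count opportunities, not rectal swabs. The documents give neither the share that might be taken rectally nor the share taken without count recovery.

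**The case against.** The strongest reply is that one word is being read apart from its context. The technique sentence sets out two alternatives only, the label allows two sources, and Section 7.2.1 fixes the method as peri-rectal or stool. A site reading all of this would not insert a swab. No specific harm has been shown either: the documents do not compare rectal with peri-rectal sampling and give no caution about rectal swabs in neutropenic children. Most follow-up samples should come after count recovery. Some text was not available, namely the consent pages and whatever stands between 13.1.2 and 13.1.4. The word may even be deliberate, since reference 57, cited in Section 7.2.1 in support of peri-rectal swabs, covers both perirectal and rectal swabs in its title.

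Much of this stands. Misuse is unlikely, the likely explanation is an editing slip, and the greater invasiveness is inferred from the ordinary meaning of the words. Nothing is claimed about what families or sites were told in the unavailable pages. What the reply does not do is reconcile the two texts: the opening instruction still lists a sample that the design does not include. If the word was intended, 13.1.1 is incomplete, because it would need a technique, a label category and matching wording in Section 7.2.1. Either way the section needs an edit.

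**Conclusion.** The concern holds as a minor inconsistency in an operative instruction. One sentence lists a rectal swab, while 15 other places in the available text provide only for stool or peri-rectal specimens. Read literally, it permits an optional research sample more invasive than the plan describes, in children some of whom have not recovered their counts.

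The likelihood is low and the number affected is unknown and probably small. Only the optional resistance study is involved. No effect is claimed on accuracy, bias between arms, participation, power or the bacteremia endpoint. The conclusion rests on the ordinary meaning of rectal as against peri-rectal and on the available text alone.

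**What to change.** At the next amendment, delete the word rectal from the first sentence of Section 13.1.1, add a short sentence stating that the swab is not to be inserted into the rectum, and send sites a brief notice. The explicit statement is worth adding because deleting the word would not by itself correct a practice that a site may already have adopted.

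The cost is one word removed, one sentence added, the usual site review of the amendment, and the notice. The change applies to future samples only; samples already collected are unaffected. The label in 13.1.2, the visits, the sample size and the analysis stay as they are.

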## 13.1.2 Specimen Labeling

Label each specimen with the following information:

- D.O.C. = date of specimen collected
- Source = Type of specimen (stool or peri-rectal swab)
- COG ID = Patient's COG ID number
- Institution = Name of institution
- Initials = Initials of person collecting specimen

## 13.1.4 Special Instructions

- If shipping on Monday, Tuesday or Wednesday please chose second day air shipping option. For example if shipping on Monday the package needs to arrive by Wednesday.
- If shipping on Thursday please chose standard overnight to arrive by Friday.

- For specimens collected on Friday, Saturday or Sunday please refrigerate the sample and wait until Monday to ship.
- Please do not ship on a holiday or the day before a holiday.
- If you need to store your specimens please store in a refrigerator at 5 to 10°C.
- For any inquiries contact [name] at [contact] or [name] at [contact].

## 13.2 Sample Processing

Upon receipt, each swab will be streaked onto the first quadrant of Colistin Naladixic Acid (CNA) agar (screening for *S. mitis*) and then on to MacConkey agar (screening for the 3 Gram negative rods of interest) and incubated in ambient air at 37°C for a minimum of 24 hours. Plates with no growth at 24 hours will be re-incubated for an additional 24 hours. When present, *E. coli, K. pneumoniae*, *P. aeruginosa* and *S. mitis* will be identified from the MacConkey agar or CNA agar plate using standard analytical profile index testing strips (specifically API E20 test kits). *S. mitis* was chosen as the representative species for all viridans group streptococci as it is the most frequently isolated species.

Sensitivity, intermediate and resistant status will be established for each Gram negative isolate to cefepime, imipenem, and levofloxacin and for each *S. mitis* isolate to cefepime, levofloxacin, and penicillin by E-test in accordance with guidelines from the Clinical Laboratories Standards Institute. Table 1 displays the breakpoints to be used to determine sensitivity, intermediate and resistant status for each organism by each antibiotic.

**Table 1.** Interpretations of MIC's (μg/mL) to establish sensitive (S), intermediate (I), and resistance (R) status for each antibiotic by colonizing organism.

Antibiotic Agent	Streptococcus mitis	Escherichia coli	Klebsiella pneumoniae	Pseudomonas aeruginosa
Levofloxacin	S: ≤ 2	S: ≤ 2	S: ≤ 2	S: ≤ 2
	I: 4	I: 4	I: 4	I: 4
	R: ≥ 8	R: ≥ 8	R: ≥ 8	R: ≥ 8
Cefepime	S: ≤ 1	S: ≤ 8	S: ≤ 8	S: ≤ 8
	I: 2	I: 16	I: 16	I: 16
	R: ≥ 4	R: ≥ 32	R: ≥ 32	R: ≥ 32
Imipenem	N/A	S: ≤ 1	S: ≤ 1	S: ≤ 1
		I: 2	I: 2	I: 2
		R: ≥ 4	R: ≥ 4	R: ≥ 4
Penicillin	S: ≤ 0.12	N/A	N/A	N/A
	I: 0.25-2			
	R: ≥ 4			

For each enrolled research subject, the second stool or perirectal swab will also be utilized to perform additional screening for the presence of carbapenem-resistant Enterobacteriaceae. These second swab specimens will be streaked on to Oxoid Brilliance Carbapenem-resistant Enterobacteriaceae agar (Oxoid Limited, United Kingdom). This media selects against growth of Gram positive bacteria and selects for growth of Gram negative bacteria with decreased susceptibility to carbapenems. The carbapenem-resistant Enterobacteriaceae plates will be incubated in ambient air at 37°C for a minimum of 24 hours. Carbapenem-resistant Enterobacteriaceae plates with no growth at 24 hours will be re-incubated for an additional 24 hours. Colonies that grow are presumed to be Gram negative bacteria and will undergo subsequent formal identification (using API E20 test kits) and susceptibility testing against meropenem, imipenem and ertapenem by E-test in accordance with guidelines from the Clinical Laboratories Standards Institute to determine presence or absence of carbapenem resistance.

